All Baseline imaging and medical/cognitive assessments must take place within a 1-week timeframe. These Baseline assessments must be completed at least 7 days before initiation of the intervention. Typically, the Baseline assessments will be completed during a single visit, lasting 4 to 5 hours.

The following assessments will be performed at the Baseline Visit:

The **Study Coordinator** will complete:

- Concomitant Medications (update of previously recorded medications)
- Adverse Event Monitoring (to capture a new or a worsening ongoing condition)
- Repeat of MRI (and rTMS) Safety form
- MRI scan: 40 minutes of scan-time, which includes:
 - Scout and calibration scans
 - 3D T1-weighted anatomical scan
 - T2-weighted FLAIR (Fluid-Attenuated Inversion Recovery) T2 GRE (Gradient Recalled Echo)
 - ASL (Arterial Spin Labeling) perfusion MRI
 - Task-free/resting-state functional MRI (rs-fMRI) using Simultaneous Multi-Slice (SMS) acquisition
 - DTI (Diffusion Tensor Imaging; 25 directions)
- Cognitive Assessments - Order of Testing
 - Montreal Cognitive Assessment (MoCA) (Nasreddine et al., 2005);
 - California Verbal Learning Test (CVLT-II) (Delis et al., 2000);
 - Brief Visuospatial Memory Test-Revised (BVMT-R) (Benedict et al., 1996)
 - Trail Making (Partington & Leiter, 1949; Reitan, 1958)
 - CVLT-II Long-Delay Free Recall and Recognition
 - BVMT-R Delayed Recall and Recognition

<Rest Break>

- Cognitive Assessments - Order of Testing
 - Boston Naming Test (BNT; Huff et al. (1986) 42 items, two equivalent forms)
 - Rey-Osterrieth Complex Figure copy task only (ROCF copy) (Hubley, 2010; Hubley & Jassal, 2006)
 - Category Fluency (boys' names; girls' names) (Strauss et al., 2006)
 - Attentional Network Task (ANT) (Fan et al., 2002; Posner, 2012; Y.-F. Wang et al., 2015)

<Rest Break: Snack or Lunch>

The **Participant and Study Partner** will independently complete the Everyday Cognition (ECog) questionnaire (Farias et al., 2008).

The **Study Partner** will complete the Functional Assessment Questionnaire (FAQ) (Pfeffer, Kurosaki, Harrah, Chance, & Filos, 1982).

Brief Descriptions of Behavioral Assessments

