6.2.4 Follow-up Visits (Visits 13, 14 and 15)

Immediate Post-Treatment (Visit 13)

The Immediate Post-Treatment Visit 13 needs to occur 7 ± 3 days after the 20th and final intervention session.

- Each of the assessments and procedures performed at the Baseline Visit will be repeated at this visit. See Section 6.2.2.

- In addition, the participant and study partner will be asked to complete a brief questionnaire regarding their views on the acceptability of rTMS as a treatment.

Follow-up at 3-Month (Visit 14)

Visit 14 can be completed ± 2 weeks of the target date.

- Vital Signs
- Concomitant Medications
- Adverse Events
- Cognitive Assessment Battery, administered by the Study Coordinator
- ECog and FAQ Functional Outcome Questionnaires completed by Participant and/or Study Partner

6-Month Follow-up (Visit 15)

Visit 15 can be completed ± 2 weeks of the target date.

- Each of the assessments performed at the 3-Month Follow-up will be repeated.
- The Study Completion/Participant Withdrawal Form will be filled out to document the participant's completion of the study.

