7.3 Adverse Events and Serious Adverse Events

Definitions for Adverse Events (AEs)

An **Adverse Event (AE)** is any untoward medical occurrence, including any abnormal sign, symptom, or disease *temporally* associated with study participation, whether or not considered related to participation in the research.

- An AE is deemed to be associated with the use of the study device if there is "a reasonable possibility that the experience may have been caused by the device."
- Chronic problems which are unchanged from baseline are not considered AEs. However, worsening of an ongoing condition would be considered an AE.

A **Serious Adverse Event (SAE)** is an adverse event that

- results in death

- is life-threatening, or places the participant at immediate risk of death from the event as it occurred
- requires or prolongs hospitalization
- leads to persistent or significant disability or incapacity
- is a seizure (Note: intervention-specific SAE definition)
- Is another condition which investigators judge to represent significant hazards.

An **Unanticipated Adverse Device Effect (UADE)** is an SAE caused by or associated with a device, if that effect, problem, or death was not previously identified in nature, severity, or degree of incidence, or any other unanticipated serious problem associated with a device that relates to the rights, safety, or welfare of patients.

Time span of collecting AEs and SAEs

Collection of all adverse events will begin at the time the participant signs the informed consent form and will continue throughout the 6-month post-intervention follow-up phase:

- At the Baseline visit, the participant and study partner (SP) will be asked about changes in medications, any other health or behavior changes, and any medical care received since the Screening visit;
- At each Intervention session, the participant will be asked about any side effects experienced. At each morning Intervention session, the participant will additionally be asked about any changes in medications, any other health or behavior changes, and any medical care received;
- At the Immediate Post-Intervention Follow-up visit, the participant will be asked about any side effects experienced since last seen, and any changes in medications, any or other health or behavior changes since the previous visit or phone follow-up, and any medical care received;

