- Patient previously had similar reaction when exposed to the treatment, and
- Reaction confirmed by objective evidence.

Study-relatedness criteria.

- All adverse events or effects with a clear causal relationship to the intervention or to the procedures involved in the research should be considered "**Definitely related**".
- All adverse events or effects with a possible causal relationship to the intervention or to the procedures involved in the research should be considered "**Possibly related**".
- In general, if event is determined to be caused solely by an underlying disease, disorder, or condition of the subject, or due to other circumstances unrelated to either the research or any underlying disease, disorder, or condition of the subject, it would be considered "**Unrelated**" to participation in the research.

Study Staff Responsibilities

- During the pre- and post-intervention phase of the study, the Study Coordinator will be responsible for collection of initial AEs, follow-up of AEs (see Section 7.5) and completion of AE forms.
- The TMS Operator will be responsible for initial AE collection, follow-up, and form completion during the intervention phase.
- The Study Physician will be responsible for reviewing all AEs and for making decisions regarding relatedness and severity.
- The PI will be responsible for reviewing the AE forms for completeness and accuracy, for monitoring the AE data to avoid double capture of AEs, and for monitoring charts and CRFs for documentation of the physician's review of AEs.

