8.2 Temporary discontinuation of the study intervention

The intervention will be temporarily discontinued in case of a concern regarding safety or intolerance to rTMS.

Recognized safety concerns for eligible participants during intervention are:

- Insufficient sleep;
- Use of substances or medications that increase seizure risk.

Tolerability concerns include:

- In case of headache or site application discomfort or other AE, the intervention can be temporarily discontinued either at the request of the participant or based on a physician's recommendation.

Modifications to the intervention schedule. In the event of a safety concern, the Study Coordinator or TMS Operator will alert the Study Physician before proceeding with rTMS. If the participant reports having had less than one hour of sleep the previous night, the rTMS session will be postponed until the participant's sleep pattern improves. If it is determined that a participant is using or abusing substances or medications that increase risk of having a seizure, the Study Physician and PI will evaluate the situation and determine if it is appropriate for the participant to continue.

While a participant is temporarily discontinued from receiving the intervention, the Study Coordinator will be responsible for phone follow-ups to check on the participant's well-being and, if applicable, to collect information regarding resolution and/or occurrence of adverse events.

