9.4 Outcomes

Outcome measures will be collected by blinded staff (study coordinator, imaging analyst, laboratory staff), and analyzed at study completion by the Database Manager under the supervision of the Ph.D. biostatistician.

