Assessments Training. The Study Coordinator will be trained in the administration and scoring of the behavioral assessments by the PI. Training will take place in three phases: self-study of the test manuals; practice in administering and scoring the assessments with a trained study coordinator (e.g. the ADNI 3 coordinator), and finally observation by PI to check for adherence to the test manuals. The PI and other staff at the study site who will provide training are experienced in administering these same assessments.

Training of Specific Assessments: CDR. The CDR rater in this study will be another researcher at the study site, so that the CDR—which is part of the screening visit diagnostic evaluation—will be collected independently of the outcome measures. The CDR rater will be certified through Washington University. If the rater has never been CDR certified, full certification will be required. The training includes nine (9) reliability tapes. The ratings/scores are compared to the Gold Standard and, if the rater passes, Washington University will issue a certificate. CDR Certification and Refresher Course can be found online at url: <http://alzheimer.wustl.edu/cdr/application/step1.htm>

Experienced MIRECC personnel associated with the Study Protocol. The following long-time study staff have worked on NIH- and VA-funded protocols that involve similar populations, assessments, biomarkers, and/or interventions (e.g. rTMS clinical trials, older adults, and cognitive outcomes):

[name], Database Manager and SAS Programmer (15% FTE). [name] is presently studying for a Master's in Statistics and has used SAS professionally for over 9 years. She and the PI have worked together 6+ years on cognitive and MRI datasets. She has performed complex analyses, including multiple linear regression modeling and mixed-effects growth curve modeling under the supervision of [name].

She has substantial experience in database management, gained under the direction of [name], the MIRECC Senior Data Manager. [name] will perform randomization of the subjects to treatment arms, to ensure that all other research staff are blinded. [name] will be responsible for setting up REDCap study database for the Study Coordinator to enter screening and other behavioral data. She will also be responsible for dataset merges in SAS and coding the data analyses and models involving the primary and secondary outcome measures.

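### The blinded CVLT-II rater also takes AE and side-effect histories, so potentially unblinding information can arrive before the primary outcome is measured

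*Combined protocol and SAP*

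**What the plan says.** - **The rater is described as blinded.** Section 9.4: "Outcome measures will be collected by blinded staff (study coordinator, imaging analyst, laboratory staff".
- **The Coordinator is the rater.** Section 10.3.1: "The Study Coordinator will be trained in the administration and scoring of the behavioral assessments by the PI". Section 6.2.2 lists the cognitive battery among the Coordinator's tasks, and 6.2.4 names the Coordinator as tester at the 3-month visit.
- **The Coordinator also collects AEs.** Section 7.4 (Study Staff Responsibilities): "During the pre- and post-intervention phase of the study, the Study Coordinator will be responsible for collection of initial AEs". AE follow-up and form completion in those phases belong to the same role.
- **AE collection falls at the primary visit.** The Coordinator's Baseline list in 6.2.2 has "Adverse Event Monitoring (to capture a new or a worsening ongoing condition" as its second item, ahead of the MRI and the CVLT-II. For Visit 13, 6.2.4 says: "Each of the assessments and procedures performed at the Baseline Visit will be repeated at this visit". Section 7.3 adds that at this visit "the participant will be asked about any side effects experienced since last seen", and that unresolved AEs are reviewed at every encounter.
- **The Coordinator makes the calls.** During a treatment pause, 8.2 says "the Study Coordinator will be responsible for phone follow-ups", including, where applicable, AE information. Sections 8.1 and 8.3 give the Coordinator similar calls after permanent discontinuation, and after withdrawal with an AE that began during treatment.
- **Safeguards.** During treatment, 7.4 says: "The TMS Operator will be responsible for initial AE collection, follow-up, and form completion during the intervention phase". Section 5.3 describes an unlabelled active/placebo coil, scalp current in the sham arm and white noise.

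**The concern.** The CVLT-II is administered and scored by an examiner. Prompting, encouragement and the handling of borderline responses can drift with what the examiner believes about assignment. Calling the rater blinded protects the primary comparison only if clues to assignment are kept from that person until testing is over. In the visible text, the person whose blinding matters most is also told about side effects and intolerance, and nothing requires testing to come first. At stake is assessor bias in both primary ANCOVAs, which rest on this one rating at Visit 13.

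**Working it through.** The plan gives no figure for this point, so the check is mainly a comparison of passages. Some arithmetic on assumed inputs follows, to show what the risk depends on.

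**1. Roles.** Sections 9.4, 10.3.1 and 6.2.2 make the Coordinator the blinded rater and scorer. Section 7.4 makes the Coordinator the AE collector outside the intervention phase. The visible text provides no separate CVLT-II rater, no rule to test before asking about AEs, and no check of rater blinding.

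**2. Visit 13.** AE monitoring is listed before testing, and Visit 13 takes over that list by reference. The label that sets a testing order covers only the cognitive tests, so the AE-first sequence is a listing and not a rule. It is permitted and looks natural, but it is not required. The Visit 14 list, repeated at Visit 15, also places medications and AEs before the battery.

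**3. Phone contacts.** This route does not depend on list order. A participant who stops because a side effect was not tolerated is called by the Coordinator (8.1) and encouraged to return for Visits 13 to 15. The primary population in 9.5.1 includes everyone randomized who started at least one session, so these participants are analysed if tested. For pauses, 8.2 also departs from 7.4: a pause lies within the intervention phase, where 7.4 gives AE follow-up to the TMS Operator.

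**4. How informative a side effect is.** The Précis gives a 2/3 chance of active treatment. If a given event is r times as frequent on active as on sham, then

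P(active | event) = 2r / (2r + 1).

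| Assumed r | P(active given event) |
|---|---|
| 1 | 2/3 = 66.7% |
| 1.5 | 3/4 = 75.0% |
| 3 | 6/7 = 85.7% |

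If sham imitates active perfectly (r = 1), the event tells the rater nothing. The documents give no sham rates, so r is unknown.

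**5. How large a bias would have to be to matter.** First, the plan's own power (9.2): d = 0.8 with two tests, taking 0.05/2 = 0.025 per test (Bonferroni is an assumption). A two-sample t-test needs 31 per group for 80.0% power, and 31/(1 - 0.06) = 32.98, or 33 with the 6% attrition cited in 9.2. With all 33 evaluable, power is 82.7%. The stated 80% is reproduced.

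In the same framework with no true effect, an assumed net rating shift toward active changes the rejection rate per test as follows.

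| Assumed shift (SD) | Rejection per test |
|---|---|
| 0 | 2.5% |
| 0.1 | 3.7% |
| 0.2 | 7.5% |
| 0.3 | 14.8% |

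These shifts are group averages over all participants, including those who give the rater no clue. The documents offer no basis for choosing a row.

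**The case against.** A reader might infer that the rater is in effect unblinded, or that the rates in 2.2 (headache up to 30%, site discomfort 15%) are what the Coordinator will hear at Visit 13. The documents do not support either reading.

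- Those rates are given as risks of rTMS, not of the post-treatment interval. The Visit 13 question covers the time since the participant was last seen, normally the 7 ± 3 days after Session 20, when no stimulation is given.
- Side effects during treatment are asked about at each session and go to the TMS Operator. Section 5.2 expects tolerance to develop over the first 5 to 10 sessions.
- Sham participants receive scalp current meant to imitate stimulation, so similar complaints may arise in both arms.
- Treatment pauses also cover insufficient sleep and seizure-risk substances or medications, so a call does not always signal intolerance.
- The outcome is a count of recalled words from a fixed 16-word list. Administration is checked against the manuals in training (10.3.1), and totals are computed automatically (10.3.2).

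All of this stands, and it makes the risk smaller and uncertain. It does not close the routes that remain: unresolved AEs reviewed at Visit 13, late-onset complaints, and the calls under 8.1, 8.2 and 8.3. Automatic totals do not control prompting or the judgement of single responses.

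The separate CDR rater in 10.3.1 should not be read as a precedent. The CDR is rated only at screening, before treatment, and its rater is kept separate because the CDR belongs to the diagnostic evaluation.

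**Conclusion.** The point holds in a limited form. The blinded rater of the primary outcome has AE duties through which potentially unblinding information can arrive before the CVLT-II is given at Visit 13. Existing safeguards reduce the risk but do not remove it. Its size cannot be estimated: the documents give no sham AE rates, no count of participants likely to be called, and no measure of how rater belief moves the score. The tables above show only what the answer depends on.

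The conclusion rests on the visible text. Appendices that are not shown could contain further masking steps. It does not show that the rater will be unblinded or that the primary result will be biased. This is a minor improvement, worth making because it is cheap and gives the blinded-assessor statement in 9.4 written support.

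**What to change.** 1. **Section 6.2.4.** State that at Visits 13, 14 and 15 the cognitive battery is completed before any AE, side-effect or concomitant-medication question, including the review of unresolved AEs. Medications belong in the rule because 5.2 expects headache to be self-treated, so the medication history could reveal the same thing. The MRI safety form is a separate item and stays before the scan.
2. **Sections 7.4, 8.1, 8.2 and 8.3.** Assign the AE phone contacts for paused, discontinued or withdrawn participants to existing staff who do no outcome testing, such as the TMS Operator. This also brings 8.2 into line with the division of work in 7.4. The content and timing of the contacts need not change.

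The cost is a small shift of staff time, which the documents do not price. Sample size, analysis and treatment procedures are unaffected. One limit remains: by Visits 14 and 15 the Coordinator will have heard the Visit 13 history, so protection there is partial. Those visits carry secondary outcomes.

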7.5 Follow-up of Adverse Events

All AEs will be followed until resolution, or until the patient's participation in the study ends. For a participant who ends study participation prior to the 3-month follow-up visit (Visit 14), unresolved SAEs/UADEs will be monitored and reported for 30 days after the date the participant was last-seen.

An AE will be considered “**resolved**” when one of the following criteria are met:

- Health has returned to baseline status or applicable variables have returned to normal.
- The event has stabilized and the study staff expect no further improvement or worsening of the event.

If the Adverse Event does not resolve and it has been determined that the condition is stable or chronic, then the event can be considered “resolved with sequelae”.

The study staff are also responsible for following up on AE/SAE information that was initially incomplete. Whenever new information about an SAE is obtained, the staff is responsible for reporting the follow-up information as soon as it becomes available.

Examples of incomplete AE/SAE information that may require follow up:

- An event for which complete information was not available at the time of reporting to the DSMB or NIA Program Official.
- Update or new information related to an event that was previously reported (e.g. receipt of hospitalization records, clarity from study participant on event details).

7.6 Safety Monitoring and other DSMB Reporting

The PI will be responsible for ensuring participants' safety on a daily basis. The Data and Safety Monitoring Board (DSMB) will act in an advisory capacity to the NIA Director to monitor participant safety, evaluate the progress of the study, to review procedures for maintaining the confidentiality of data, the quality of data collection, management, and analyses. The DSMB will also determine when they should be un-blinded to treatment assignment for the reviewing of AE data and evaluating whether the aggregate AE information may also qualify as a UP. The DSMB will advise the PI concerning whether the study should continue or be stopped for safety reasons.

DSMB will meet twice annually, typically by teleconference call to review study progress, data quality, and participants' safety. The DSMB may decide to meet less frequently (such

as annually) and may receive a data report for their review in-between meetings. The DSMB will discharge itself from its duties when the last participant completes the study.

Open-Session Reports to the DSMB will include information on: (1) recruitment and overall study status; (2) participants descriptive information; (3) safety information, and (4) information on study quality. The contents of the report will be based on the NIH Single-site Open DSMB Reports Templates. Appendix IX “Data and Safety Monitoring” provides an outline of the various tables and charts that the PI proposes to provide to the DSMB. For example, a recruitment-related table will show the reasons for screen failures, including any refusals to donate blood or saliva for DNA extraction.

For Closed-Session reports, the Study’s Data manager will generate AE reports using modified NIA templates with information reported by blinded treatment group (A, B, C). The final content and format of the reports for both the open and closed sessions will be determined by the DSMB. Throughout the trial, the DSMB may request changes in the content or format of the reports.

Special Procedures for the Monitoring of Seizures

As addressed in the rTMS Safety Section 7.1.1, participants will be closely monitored by the study physician and the certified TMS operator during the intervention phase to minimize the risks associated with the rTMS intervention/device. In the unlikely event that a seizure occurs, the hospital where this rTMS study will be conducted is fully equipped and staffed to respond to a seizure. The study staff will be trained as first responders, and trained to carry out the “Seizure Protocol” previously developed by the CSP 556 investigators (see Appendix VI). Procedures for medical care, for documenting and reporting this study-specific SAE, and for monitoring the outcome of a seizure-related SAE are described separately in the seizure safety protocol.

